6.5 SAFETY ANALYSES

All safety data will be reported in individual listings and summarized by assessment time using descriptive statistics. Data collected during the follow-up period (i.e., after discontinuation of study treatment) will be summarized separately from the data collected during the treatment period.

All verbatim adverse event terms will be mapped to MedDRA thesaurus terms and adverse event severity will be graded according to [Table 3](#). The incidence of adverse

events will be summarized on the basis of body systems, dictionary-preferred terms by severity and relationship to study drug.

[REDACTED]

[REDACTED]

Treatment-emergent abnormalities from physical and neurological examinations will be listed by treatment and subject to statistical analysis where applicable.

6.6 EFFICACY ANALYSES

All exploratory efficacy data from baseline and following visits as well as participants' demographics and baseline characteristics (age, sex, comorbidities, pharmacological and non-pharmacological treatment etc.) will be listed and summarized using descriptive statistics providing means, medians, standard deviations, and range values.

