3. STUDY DESIGN

3.1 DESCRIPTION OF THE STUDY

This is a Phase Ib, multicenter, open-label study in children 2–4 years old with ASD to investigate the pharmacokinetics, safety, and tolerability of an oral dose of 4 mg balovaptan QD, which is predicted to *be adult-equivalent, i.e., provide a plasma exposure range that is comparable to that following oral doses of 10 mg balovaptan QD in adults*. The study consists of a 6-week treatment period to evaluate the pharmacokinetics of balovaptan in 2- to 4-year old children followed by an optional extension period of 48 weeks.

Subjects for whom consent has been provided by their parent or legal guardian will undergo screening within 4 weeks prior to the first study drug administration. Eligible subjects will be enrolled in an open-label fashion and treated with 4 mg balovaptan.

The safety of balovaptan will be assessed by monitoring of adverse events, serious adverse events, clinical laboratory values, ECGs, physical and neurologic examinations, and safety outcome assessments such as suicidality. Exploratory efficacy endpoints will examine core autism symptoms (social interaction, social communication) and functional deficits.

The total duration of the study (from screening through to study completion) for each subject will be approximately 12 weeks or 60 weeks, depending on whether or not he or she participates in the optional extension period, divided as follows:

[figure not shown]
- Screening period: approximately 4 weeks
- Treatment period: 6 weeks
- Optional extension period: 48 weeks
- Post-treatment follow-up period: 2 weeks

Approximately 10 subjects will be enrolled at approximately 10 international sites, including sites in North America and Spain. A subject may be replaced in the event that the subject's treatment is discontinued for any reason during the 6-week treatment period.

Enrollment will be based on the selection of two age groups (children 3–4 years old vs. children 2 years old). The targeted ratio between the age groups will be approximately 2:1 (children 3–4 years old to children 2 years old; e.g., 7 children 3–4 years old and 3 children 2 years old if 10 subjects are enrolled). This ratio may change based on the ability to recruit children in both age groups and based on observed exposures levels of balovaptan and its metabolites.

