3.1.4 Optional Extension Period

All subjects who complete the 6-week treatment period, and in the view of the investigator, have not experienced relevant adverse events considered prohibitive for further treatment are eligible for participation in the extension period of the study. The transition into the extension period is seamless; subjects will continue to receive study drug treatment without interruption after the end of the 6-week period. Subjects who do not participate in the extension period of the study will complete the follow-up visit 2 weeks after their final dose (see Section 3.1.5).

The 48-week duration of the extension period serves to evaluate the long-term safety, tolerability, and exploratory efficacy of balovaptan treatment in young children with ASD. All subjects will continue to receive an oral dose of 4 mg balovaptan QD, which is predicted to be equivalent to the adult oral dose of 10 mg balovaptan QD. If a change in dose occurs, all subjects in the 6-week treatment period and all subjects in the extension period will receive the new dose at the earliest opportunity (see Section 3.1.3). For the schedule of activities to be performed during the extension period, see [REDACTED].

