3.3.4 Rationale for Extension Period

The study will include an optional 48-week extension period to evaluate effects of balovaptan in young children over a longer time period. The extension period of 48 weeks will give subjects and their families the option to continue treatment with balovaptan and will add to the long-term safety information as well as provide the first, preliminary indicators of efficacy of balovaptan in this age group.

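### Section 6.6 plans no same-child comparison for efficacy visits after Week 6, so a trend in visit means may reflect which children entered the optional extension

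*Combined protocol and SAP*

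**What the plan says.** Section 2.3 lists the exploratory efficacy endpoints (Vineland-II two-domain composite, CGI-S, CGI-I, CaGI-C and CaGI-S), each as change from baseline at Weeks 6, 12, 24 and 54.

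Section 3.1 gives the size and timing: "Approximately 10 subjects will be enrolled at approximately 10 international sites", with six weeks of treatment and then "Optional extension period: 48 weeks".

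Section 3.1.4 opens the extension to children who complete the six weeks and who, in the investigator's view, "have not experienced relevant adverse events considered prohibitive for further treatment". For the others it says: "Subjects who do not participate in the extension period of the study will complete the follow-up visit 2 weeks after their final dose". Section 3.3.4 describes continuing as the family's option and expects the extension to "provide the first, preliminary indicators of efficacy of balovaptan in this age group".

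Section 6.6 is the whole efficacy analysis: data from baseline and later visits "will be listed and summarized using descriptive statistics providing means, medians, standard deviations, and range values". It states no analysis set, no rule for missing or early-termination data, and no summary restricted to children who entered the extension. The opening of Section 6 leaves further detail to a Statistical Analysis Plan; the text available contains only the protocol's Section 6.

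**The concern.** The children who can contribute at Weeks 12, 24 and 54 have passed three filters after baseline: completing six weeks, the investigator's adverse-event judgement, and the family's choice. The study is open-label and single-arm. The caregiver is also the informant for the Vineland-II and completes the CaGI-S and CaGI-C (Section 4.5.11, Table 1), so families hold a view of how the child has done. Section 3.3.1 presents the extension as an opportunity of possible benefit. A link between perceived response and continuing is therefore plausible, though not documented.

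If such a link exists, a table of visit means would compare a wider group at Week 6 with a more favourable subset later. The means could then appear to improve (higher Vineland-II; lower CGI-S, CGI-I, CaGI-S and CaGI-C) while every child stayed where they were at Week 6. At stake is how the first efficacy indicators in this age group are read. The primary pharmacokinetic result is not affected.

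**Working it through.** **No figure to reproduce.** The plan gives no sample size, power, effect size or expected extension uptake for efficacy. The steps below check whether the mechanism follows from the text, and how large it could be.

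**Step 1: timing.** Six weeks of treatment plus 48 weeks of extension is 6 + 48 = 54. Weeks 12, 24 and 54 all fall in the extension. Section 3.1.4 describes only a two-week follow-up visit for children who do not enter, so no later efficacy value is planned for them.

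**Step 2: a worked example with no change after Week 6.** Take ten illustrative changes from baseline: −6, −4, −2, 0, 1, 2, 3, 4, 5, 7.
- Week 6 mean of all ten: 10/10 = 1.00.
- Suppose the three lowest do not continue. The later mean of the remaining seven is 22/7 = 3.14.
- Apparent gain: 3.14 − 1.00 = 2.14 points.
- The same seven children's own Week 6 mean is also 3.14, so the same-child gain is 0.00.

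**Step 3: expected size for n = 10.** Assume that each child's change is normally distributed and fixed after Week 6. Let the k children who continue be those with the highest values of a score that has correlation rho with the change. The expected shift, mean of continuers minus mean of all ten, is

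shift = rho × m(k),

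where m(k) is the expected mean of the k largest of ten standard normal values. A simulation of 200,000 runs gave, in SDs of change:

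| Continuing | rho 0 | rho 0.3 | rho 0.5 | rho 0.7 | rho 1.0 |
|---|---|---|---|---|---|
| 9 of 10 | 0.00 | 0.052 | 0.085 | 0.120 | 0.171 |
| 8 of 10 | 0.00 | 0.095 | 0.159 | 0.223 | 0.318 |
| 7 of 10 | 0.00 | 0.137 | 0.228 | 0.320 | 0.457 |
| 6 of 10 | 0.00 | 0.179 | 0.297 | 0.417 | 0.596 |
| 5 of 10 | 0.00 | 0.221 | 0.370 | 0.517 | 0.739 |

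Check: 0.3 × 0.457 = 0.137. If all ten continue, the shift is 0 whatever rho is. A negative rho gives the same sizes with the sign reversed.

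**Step 4: in Vineland-II points.** Section 4.5.11.2 gives a norm SD of 15 for scores, but no SD of change. Assuming an SD of change of 5, 8 or 10 points and 7 of 10 continuing:
- rho 0.3: 0.137 × 5, 8, 10 = 0.7, 1.1, 1.4 points.
- rho 1.0: 0.457 × 5, 8, 10 = 2.3, 3.7, 4.6 points.
- Standard error of a ten-child mean, SD/√10: 1.6, 2.5, 3.2 points.

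At rho 0.3 the shift is 0.137/0.316 = 0.43 of that standard error; at rho 1.0 it is 0.457/0.316 = 1.4 times it.

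**The case against.** The strongest reply has four parts.

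- **The plan is silent, not wrong.** Section 6.6 specifies no table layout, and Section 6 defers detail to a SAP that could add what is missing. This stands: a reader might infer that an observed-case display has been chosen, but the documents do not say so. They only fail to rule it out.
- **Much of the information will exist.** Individual data are to be listed, and with about ten children a reader can rebuild the comparison. Section 6.2 summarises reasons for premature withdrawal. Section 4.5.12 puts an exit question at Week 6 to caregivers of children who do not enter the extension. This reduces the problem but does not produce the comparison. A family that declines an optional extension is also not clearly a premature withdrawal.
- **The effect may be small.** Every endpoint is measured against the child's own baseline, so a different baseline level among continuers does not by itself create a gain. The adverse-event filter shifts mean change only if prohibitive events are related to response. At a modest link the shift is under half the standard error of a ten-child mean. All of this stands.
- **No decision depends on these means.** Efficacy is exploratory, no test or threshold uses it, and without a control arm a 54-week trend cannot separate drug effect from development or from concurrent interventions, which Section 4.4.1 lets families start or continue. This stands, and it limits the weight of the point.

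**Conclusion.** The point holds as a gap in a descriptive plan. Later visit means would come from a filtered subset of the children assessed at Week 6, and Section 6.6 includes nothing that separates a change in who is measured from a change within children. For ten children, the expected shift runs from 0 (no link, or all continue), through about 0.14 SD of change (rho 0.3, 7 continue), to 0.32 SD (8 continue) or 0.74 SD (5 continue) if continuing follows response perfectly. These sizes assume normal changes that stay fixed after Week 6. Uptake, rho and the SD of change are all assumptions.

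A reader might be tempted to go further, and the documents do not support it:
- **That Week 6 means include all children.** Children who stop before Week 6 may be replaced (Sections 3.1 and 4.6.1) and need not have a Week 6 value.
- **That families choose after seeing the six-week result.** Section 3.1.4 calls the transition seamless and does not say when or on what basis they decide.
- **That an apparent trend will be pure selection.** That requires continuing to be related to response and no real change after Week 6.
- **That the shift could be 0.80 SD (half continue) or 0.35 SD (80% continue).** These are large-sample maxima, 0.399/0.5 and 0.280/0.8; the values for ten children are lower.

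**What to change.** In Section 6.6 or the SAP:

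1. Show n for every endpoint at every visit, and state how missing and early-termination values are handled.
2. Beside each Week 12, 24 and 54 summary, show the Week 6 change (for CGI-I and CaGI-C, the Week 6 rating) of the same children. Redefine the set at each visit so that later dropout is covered too.
3. Show Week 6 change separately for children who did and did not enter the extension, with reasons for not continuing.
4. Describe trends over time only within the same-child sets.

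The cost is one additional descriptive table from efficacy data already planned. If the eCRF does not record why a family declined the extension, one field is needed. No visit, sample size or treatment rule changes. The table removes selection from the time trend; it does not make an uncontrolled trend attributable to the drug.

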7. DATA COLLECTION AND MANAGEMENT

7.1 DATA QUALITY ASSURANCE

The Sponsor will be responsible for data management of this study, including quality checking of the data. Data entered manually will be collected via EDC through use of eCRFs. Sites will be responsible for data entry into the EDC system. In the event of discrepant data, the Sponsor will request data clarification from the sites, which the sites will resolve electronically in the EDC system. In the event of discrepant data, the Sponsor will request data clarification from the sites, which the sites will resolve electronically in the EDC system.

The Sponsor will produce an EDC Study Specification document that describes the quality checking to be performed on the data. Central laboratory data and electronic clinical outcome assessment (eCOA) data will be sent directly to the Sponsor, using the Sponsor's standard procedures to handle and process the electronic transfer of these data.

eCRFs and correction documentation will be maintained in the EDC system's audit trail. System backups for data stored by the Sponsor and records retention for the study data will be consistent with the Sponsor's standard procedures.

eCOA data will be collected through the use of an electronic device provided by a vendor (see Section 7.3 for details).

7.2 ELECTRONIC CASE REPORT FORMS

eCRFs are to be completed through use of a Sponsor-designated EDC system. Sites will receive training and have access to a manual for appropriate eCRF completion. eCRFs will be submitted electronically to the Sponsor and should be handled in accordance with instructions from the Sponsor.

All eCRFs should be completed by designated, trained site staff. eCRFs should be reviewed and electronically signed and dated by the investigator or a designee.

At the end of the study, the investigator will receive subject data for his or her site in a readable format on a compact disc that must be kept with the study records. Acknowledgement of receipt of the data is required.

7.3 ELECTRONIC CLINICAL OUTCOME DATA

An electronic device will be used to capture eCOA data. The device is designed for entry of data in a way that is attributable, secure, and accurate, in compliance with U.S. FDA regulations for electronic records (21 CFR, Part 11). The data will be transmitted to a centralized database maintained by the electronic device vendor.

The electronic data will be available for view access only, via a secure vendor web portal. Only identified and trained users may view the data, and their actions will become part of the audit trail. The Sponsor will have view access only. System backups for data stored by the Sponsor and records retention for the study data will be consistent with the Sponsor's standard procedures.

Once the study is complete, the data, audit trail, and trial and system documentation will be archived. The investigator will receive subject data for the site in both human- and machine-readable formats that must be kept with the study records as source data. Acknowledgement of receipt of the data is required. In addition, the Sponsor will receive all data in a machine-readable format.

7.4 SOURCE DATA DOCUMENTATION

Study monitors will perform ongoing source data verification and review to confirm that critical protocol data (i.e., source data) entered into the eCRFs by authorized site personnel are accurate, complete, and verifiable from source documents.

Source documents (paper or electronic) are those in which subject data are recorded and documented for the first time. They include, but are not limited to, hospital records, clinical and office charts, laboratory notes, memoranda, patient-reported outcomes, evaluation checklists, pharmacy dispensing records, recorded data from automated instruments, copies of transcriptions that are certified after verification as being accurate and complete, microfiche, photographic negatives, microfilm or magnetic media, X-rays, patient files, and records kept at pharmacies, laboratories, and medico-technical departments involved in a clinical trial.

Before study initiation, the types of source documents that are to be generated will be clearly defined in the Trial Monitoring Plan. This includes any protocol data to be entered directly into the eCRFs (i.e., no prior written or electronic record of the data) and considered source data.

Source documents that are required to verify the validity and completeness of data entered into the eCRFs must not be obliterated or destroyed and must be retained per the policy for retention of records described in Section 7.6.

To facilitate source data verification and review, the investigators and institutions must provide the Sponsor direct access to applicable source documents and reports for trial-related monitoring, Sponsor audits, and IRB/EC review. The study site must also allow inspection by applicable health authorities.

7.5 USE OF COMPUTERIZED SYSTEMS

When clinical observations are entered directly into a study site's computerized medical record system (i.e., in lieu of original hardcopy records), the electronic record can serve as the source document if the system has been validated in accordance with health authority requirements pertaining to computerized systems used in clinical research. An acceptable computerized data collection system allows preservation of the original entry of data. If original data are modified, the system should maintain a viewable audit trail that shows the original data as well as the reason for the change, name of the person making the change, and date of the change.

7.6 RETENTION OF RECORDS

Records and documents pertaining to the conduct of this study and the distribution of IMP, including eCRFs, electronic or paper PRO and ObsRO data (if applicable), Informed Consent Forms, laboratory test results, and medication inventory records, must be retained by the Principal Investigator for 15 years after completion or discontinuation of the study or for the length of time required by relevant national or local health authorities, whichever is longer. After that period of time, the documents may be destroyed, subject to local regulations.

No records may be disposed of without the written approval of the Sponsor. Written notification should be provided to the Sponsor prior to transferring any records to another party or moving them to another location.

Roche will retain study data for 25 years after the final study results have been reported or for the length of time required by relevant national or local health authorities, whichever is longer.

8. ETHICAL CONSIDERATIONS

8.1 COMPLIANCE WITH LAWS AND REGULATIONS

This study will be conducted in full conformance with the ICH E6 guideline for Good Clinical Practice and the principles of the Declaration of Helsinki, or the applicable laws and regulations of the country in which the research is conducted, whichever affords the greater protection to the individual. The study will comply with the requirements of the ICH E2A guideline (Clinical Safety Data Management: Definitions and Standards for Expedited Reporting). Studies conducted in the United States or under a U.S. Investigational New Drug (IND) Application will comply with U.S. FDA regulations and applicable local, state, and federal laws. Studies conducted in the European Union or European Economic Area will comply with the E.U. Clinical Trial Directive (2001/20/EC), and applicable local, regional, and national laws.

8.2 INFORMED CONSENT

The Sponsor's sample Informed Consent Form (and ancillary sample Informed Consent Forms such as an Assent Form or Mobile Nursing Informed Consent Form, if applicable) will be provided to each site. If applicable, it will be provided in a certified translation of the local language. The Sponsor or its designee must review and approve any proposed deviations from the Sponsor's sample Informed Consent Forms or any alternate consent forms proposed by the site (collectively, the "Consent Forms") before IRB/EC submission. The final IRB/EC-approved Consent Forms must be provided to the Sponsor for health authority submission purposes according to local requirements.

If applicable, the Informed Consent Form will contain separate sections for any optional procedures. The investigator or authorized designee will explain to each subject or the subject's legally authorized representative the objectives, methods, and potential risks associated with each optional procedure. Subjects or the subject's legally authorized representative will be told that they are free to refuse to participate and may withdraw their consent at any time for any reason. A separate, specific signature will be required to document a subject's or subject's legally authorized representative's agreement to participate in optional procedures. Subjects or subject's legally authorized representatives who decline to participate will not provide a separate signature.

The Consent Forms must be signed and dated by the subject or the subject's legally authorized representative before his or her participation in the study. The case history or clinical records for each subject shall document the informed consent process and that written informed consent was obtained prior to participation in the study.

The Consent Forms should be revised whenever there are changes to study procedures or when new information becomes available that may affect the willingness of the subject to participate. The final revised IRB/EC-approved Consent Forms must be provided to the Sponsor for health authority submission purposes.

Subjects or the subject's legally authorized representatives must be re-consented to the most current version of the Consent Forms (or to a significant new information/findings addendum) in accordance with applicable laws and IRB/EC policy during their participation in the study. For any updated or revised Consent Forms, the case history or clinical records for each subject shall document the informed consent process and that written informed consent was obtained using the updated/revised Consent Forms for continued participation in the study.

A copy of each signed Consent Form must be provided to the subject or the subject's legally authorized representative. All signed and dated Consent Forms must remain in each subject's study file or in the site file and must be available for verification by study monitors at any time.

For sites in the United States, each Consent Form may also include subject or legally authorized representative authorization to allow use and disclosure of personal health information in compliance with the U.S. Health Insurance Portability and Accountability Act (HIPAA) of 1996. If the site utilizes a separate Authorization Form for subject authorization for use and disclosure of personal health information under the HIPAA regulations, the review, approval, and other processes outlined above apply except that IRB review and approval may not be required per study site policies.

